1. SYNOPSIS

1.1 Study Title

A Randomized, Double-Blind, Placebo-Controlled Pilot Study of Suvorexant for Insomnia in Parkinson Disease

1.2 Study Drug

Suvorexant 10-15 mg PO QHS

1.3 Study Subjects

20 subjects with Parkinson disease (PD) and insomnia

1.4 Study Design

Multiple-dose, randomized, placebo-controlled prospective, single-site, investigator-initiated trial.

1.5 Study Overview

The proposed study is a randomized, double-blind, placebo-controlled, cross-over trial to assess the safety, tolerability, and efficacy of suvorexant specifically in a cohort of 20 PD patients between the ages of 30 and 80 (inclusive) who have a complaint of insomnia. After informed consent is given, potential subjects will be screened to ensure they meet eligibility criteria. This will include an overnight polysomnogram (PSG), which will serve both as a baseline and a screening PSG. Active drug will be suvorexant 10 mg po QHS with an optional up-titration to 15 mg po QHS after 2 weeks. The first treatment period will be 4 weeks long, in which subjects will be randomized 1:1 to receive active drug or matching placebo. At the end of treatment period 1, subjects will undergo efficacy assessment with repeat PSG and clinical scales. This will be followed by a 2-week washout period with placebo; this period only will be single-blinded, as subjects only will be blinded to treatment. Subjects will then be crossed over into the alternate treatment group, which will once again be double-blinded; those on active treatment for period 1 will be switched to placebo, and those on placebo in period 1 will be switched to active treatment. Treatment period 2 will also be 4 weeks long, and at the end of this, subjects will undergo final assessment with PSG and clinical scales.

All subjects, whether in placebo or active arm, will receive a wearable sleep monitor to be worn continuously throughout the study. The subjects will be allowed to keep the wearable sleep monitor in lieu of a monetary reimbursement for Office Visit 1; subjects will receive a small monetary reimbursement per visit for each office visit after Office Visit 1.

1.6 Study Hypothesis

1.6.1 Primary hypothesis

Suvorexant will provide greater improvement in sleep, as measured by polysomnographic parameters and symptom rating scales, compared to placebo, with no clinically significant increase in adverse events.

1.6.2 Secondary Hypotheses

- On nights of PSG, total hours of sleep and WASO as measured by a wearable sleep monitor will not be significantly different from those values as measured by PSG.
- Suvorexant will not worsen motor symptoms or non-motor symptoms of PD compared to placebo; motor signs and motor and non-motor symptoms will be assessed by the Movement Disorder Society's Unified Parkinson Disease Rating Scale; specific non-motor symptoms will be assessed by the Beck Depression Inventory, the Beck Anxiety Inventory, and Montreal Cognitive Assessment; REM behavior disorder will be assessed by muscle tonicity during PSG.

1.7 Study Timeline

Each subject's participation in this study will last 11-15 weeks. This includes a 1- to 5-week screening period (depending on the scheduling of the initial PSG), two 4-week treatment periods, and a 2-week washout period between the treatment periods.

1.8 Treatment Regimen

1.8.1 Treatment Period 1

Group A will receive suvorexant 10 mg to be taken by mouth every night, at most 30 minutes before the intended bedtime and at least 7 hours before the intended time of awakening. At Phone Visit 2, those who are eligible to up-titrate will be instructed to begin taking an additional 5-mg tablet, for a total of suvorexant 15 mg by mouth every night.

Group B will receive placebo that matches suvorexant 10 mg with the same instructions. At Phone Visit 2, those who are eligible to up-titrate will be instructed to begin taking an additional placebo matching the suvorexant 5 mg tablet.

1.8.2 Treatment Period 2

The regimen will be the same as in treatment period 1 but the groups will be reversed.

1.9 Inclusion and Exclusion Criteria

1.9.1 Inclusion Criteria

An eligible patient:

- Has signed and dated an IRB-approved informed consent form before any protocol-specific screening procedures are performed;
- Has a diagnosis of Parkinson disease according to the United Kingdom Parkinson Disease Society Brain Bank Criteria (UKBB);

- Has a modified Hoehn and Yahr (mHY) Stage of 1-3, inclusive;
- Is aged 30-80 years old, inclusive;
- Has had no change in PD medications during the 4 weeks preceding screening, with no dose changes during the study, except that PRN (as needed) doses of carbidopa/levodopa will be allowed to address periodic worsening of parkinsonian symptoms;
- Is willing and able to complete PSG;
- Is willing and able to abstain from alcohol, caffeine, and marijuana for 6 hours prior to and during each study-related PSG;
- Is willing and able to abstain from products containing nicotine during each study-related PSG;
- Has Insomnia Disorder defined by diagnostic criteria published in the Diagnostic and Statistical Manual of Mental Disorders, 5th edition (DSM-5); namely, subject report of all of the following:
 - One of the following: difficulty initiating sleep; difficulty maintaining sleep; or early morning waking;
 - Sleep disturbance causes clinically significant distress or impairment in social, occupational, educational, academic, behavioral, or other important areas of functioning;
 - Sleep difficulty has occurred on 3 or more nights per week;
 - Sleep difficulty has been present for at least the past 3 months;
 - Sleep difficulty occurs despite adequate opportunity for sleep;
 - Insomnia is not explained by another sleep disorder;
 - Insomnia is not attributable to physiological effects of a consumed substance;
- On screening PSG, has a latency to persistent sleep \geq 20 minutes OR total wakefulness after sleep onset \geq 45 minutes;
- May use other medications that could influence sleep, other than those specifically prohibited, as long as the dose is stable for 4 weeks preceding screening, with no dose changes during the study; and
- Has valid health insurance coverage at the time of study enrollment and expects this coverage to remain valid for the duration of the study period.

1.9.2 Exclusion Criteria

A subject will be excluded from the study if he or she meets any of the following:

- Is a woman who is breast-feeding, pregnant, or has the potential to become pregnant during the course of the study (fertile and unwilling/unable to use effective contraceptive measures);
- Has an implanted deep brain stimulator;
- Has a history of narcolepsy;
- Has a diagnosis of severe COPD, defined by FEV1 < 50% of predicted on most recent available pulmonary function test (PFT) (a PFT is not required if the subject has never been diagnosed with COPD);

- Has a history of severe obstructive sleep apnea (OSA) or evidence of severe OSA on screening PSG, with severe OSA defined as having an apnea-hypopnea index (AHI) > 30;
- Is concurrently using other CNS depressants, including alcohol, except that one alcoholic drink per day will be allowed for those with normal hepatic function provided the drink is consumed at least 2 hours prior to or 8 hours after taking the study drug, and no alcohol will be permitted for 6 hours before PSG visits;
- Is concurrently using digoxin;
- Is concurrently using any moderate or strong inhibitor of CYP3A;
- Is concurrently using any strong inducer of CYP3A;
- Has evidence at screening of severe hepatic impairment as defined by a Child-Pugh score > 10;
- Has evidence at screening of severe cognitive impairment as defined by a MoCA score < 15, or has cognitive impairment that in the opinion of the investigator would prevent completion of study procedures or the ability to provide informed consent.
- Has evidence at screening of suicidal ideation in the past 6 months as defined by a positive response to any one of Questions 2-5 on the Columbia Suicide Severity Rating Scale (C-SSRS); or of a lifetime history of suicidal behavior as defined by any positive response to the suicidal behavior section of the C-SSRS.

1.9.3 Note on the Use of the Wearable Sleep Monitor

Of note, inability or unwillingness to use the WSM is specifically *not* an exclusion criterion. Those subjects who are unable or unwilling to use the WSM correctly will be allowed in the study (provided all eligibility criteria are otherwise met), and the observations from their WSM variables will be treated as missing data.

1.10 Efficacy Assessment

1.10.1 Primary Outcome Measure

The primary outcome measure will be sleep efficiency as measured by PSG, defined as (total sleep time / total time in bed) * 100%

1.10.2 Secondary Outcome Measures based on PSG

Secondary outcome measures based on PSG will include:

- Wake after sleep onset
- Latency to persistent sleep
- Muscle tonicity (as measure of REM Behavior Disorder)

1.10.3 Secondary Outcome Measures based on Clinical Rating Scales

The following clinical rating scales will be administered as secondary outcomes measures:

- Insomnia Severity Index
- Epworth Sleepiness Scale
- Subject's Global Impression of Change
- Clinician's Global Impression of Change.
- Montreal Cognitive Assessment
- Beck Depression Inventory
- Beck Anxiety Inventory
- MDS-UPDRS Total Score
- MDS-UPDRS Part 1 (Non-Motor) Score
- MDS-UPDRS Question 1.7 (Sleep Problems) Score
- MDS-UPDRS Question 1.8 (Daytime Sleepiness) Score

1.10.4 Secondary Outcome Measure based on Wearable Sleep Monitor

The secondary outcome measure based on the wearable sleep monitor (WSM) will include:

- Total hours of sleep per night, mean over final 7 nights of treatment period compared to mean over final 7 nights of screening period
- Wakefulness after sleep onset (WASO), mean over final 7 nights of treatment period compared to mean over final 7 nights of screening period

1.11 Statistical Methods

Analysis of primary and secondary outcome measures will include:

- Summary statistics (n, mean, standard deviation, median, minimum and maximum) at baseline, Office Visit 3 and Office Visit 5 by treatment.
- For clinical rating scales, summary of % change from baseline to Office Visit 3, from baseline to Office Visit 5, and from Office Visit 4 to Office Visit 5, by treatment
- For PSG variables, summary of % change from PSG 1 to PSG 2 and from PSG 1 to PSG 3, by treatment
- For wearable sleep monitor, summary of % change in total hours of sleep and WASO. Mean over the week prior to Office Visit 2 (baseline) will be compared to the mean over the final week of Treatment Period 1 and to the mean over the final week of Treatment Period 2. Mean over the week prior to Office Visit 4 (during washout) will be compared to the mean over the final week of Treatment Period 2. This will be done by treatment arm.
- Significance testing

The following characteristics will be summarized descriptively for placebo and drug groups:

- Demographics (age, gender, race)
- Parkinson disease characteristics at baseline (disease duration, date of onset, initial symptom, modified Hoehn and Yahr stage in the ON state, and MDS-UPDRS part 3 score in the ON state)

- Levodopa-equivalent daily dose (LEDD), calculated according to published formulae (Tomlinson 2010, Rytary Prescribing Information, Duopa Prescribing Information).

Outcome measures will be compared between groups using analysis of covariance (ANCOVA) or other method as deemed appropriate by the consulting statistician. Demonstration of superiority will depend on achieving statistical significance for the primary endpoint. Level of significance will be defined as $p = 0.05$. All statistical tests will be two-sided.

The study population will include all patients who pass screening and undergo randomization. Data will be analyzed in an intent-to-treat fashion.

This is an exploratory study. Therefore, a small sample size is appropriate. Any treatment effect could be used to power a future larger study.

Statistical analysis will be performed by a consulting statistician contracted with EvergreenHealth and whose services we have used on recent studies in PD.

1.12 Safety

Female subjects will undergo urine pregnancy testing if they are deemed to have any risk of being pregnant or becoming pregnant during the study. Baseline assessment of CBC, CMP, albumin, and INR will be conducted to address exclusion criteria.

Subjects will be monitored for adverse events throughout the trial in phone visits and office visits, both scheduled and unscheduled as needed. The occurrence of adverse events will be ascertained by observation, telephone monitoring if subjects call in, and by questioning by the investigator. Safety assessments will consist of monitoring and recording all adverse events, including serious adverse events. An adverse event is any undesirable sign, symptom or medical condition occurring after starting study drug (or therapy). Medical conditions/diseases present before starting study treatment are only considered adverse events if they worsen after starting study treatment.

Adverse events include adverse drug reactions, illness with onset during the study, exacerbations of pre-existing conditions or clinically significant changes in physical examination or significantly abnormal objective test findings. All adverse events will be recorded and graded as mild, moderate or severe by the principal investigator in accordance with general guidelines of clinical research. The principal investigator will also determine the relatedness of each adverse event to the study drug in accordance with general guidelines of clinical research.

A serious adverse event is an undesirable sign, symptom or medical condition which: 1. is fatal or life-threatening, 2. requires or prolongs hospitalization, 3. results in persistent or significant disability/incapacity, 4. constitutes a congenital anomaly or a birth defect, 5. is medically significant, in that it may jeopardize the subject and may require medical or surgical intervention to prevent one of the outcomes listed above. If any serious adverse events occur, the treatment status of the subject(s) may be revealed, as clinically indicated. Subjects who discontinue medication use will be followed for adverse events until reaching the termination of adverse

events. The frequency of adverse events (AE) will be under continuous scrutiny during the observation with comparison to AE rates that have been recorded in published PD drug trials.

1.13 Schedule of Events

Please refer to the attached Schedule of Assessments for timing of procedures.

1.14 Expected Study Timeline

Study duration is estimated at 17 months (start-up period of 2 months and enrollment period of 15 months), with an additional 2 months for data analysis and manuscript preparation.

2. BACKGROUND AND RATIONALE

2.1 Insomnia in PD

Parkinson disease (PD) is the second most common neurodegenerative disease behind Alzheimer disease. Prevalence is estimated to be 0.3% of the general population and 1% of the population over the age of 60 (de Lau 2006). It is estimated that there were over 4 million cases worldwide in 2005, and that number is expected to more than double by 2030, to 8.7 million (Dorsey 2007). Prevalence in the United States is expected to nearly double over the same time period, with a projected 610,000 cases in the US by 2030 (Dorsey 2007).

Sleep disorders are common in PD. In one community-based survey (Tandberg 1998), disrupted sleep had an estimated prevalence of 60% among PD patients, compared to 33% in the healthy elderly population. Nearly 32% of the PD patients in this study reported trouble falling asleep, 39% reported frequent awakening, and 23% reported early awakening. More than 40% reported taking a medication to help them sleep. This corresponds with findings of a more recent survey, in which nearly half of respondents scored 8 or greater on the Insomnia Severity Index (Chung 2013).

The reasons for the prevalence of insomnia in Parkinson disease are not entirely clear, but have been attributed to physical symptoms, depression, and direct effects of PD on the neural control of sleep onset and maintenance (Tandberg 1998). Since some currently used insomnia medications may adversely affect mood and PD symptoms, it is important in studies of insomnia in PD to measure the severity of motor and non-motor symptoms, especially mood.

Despite the high prevalence of insomnia in PD, there are relatively few studies specifically in PD of medications to improve insomnia. Doxepin has shown benefit (Rios Romenets 2013) and dopamine agonists may increase somnolence generally but have not been shown to specifically improve insomnia in published reports. Melatonin has shown improvement in subjective sleep quality in 2 small studies in PD but not other measures of sleep disturbance (Dowling 2005, Medeiros 2007). Clonazepam is frequently used when REM behavior disorder is present (Gagnon 2006). Other soporifics are used on the basis of standard clinical practice rather than evidence from randomized clinical trials in Parkinson disease patients.

2.2 Suvorexant for insomnia

Suvorexant (MK-4305, Belsomra®) is a recently FDA-approved medication for the treatment of insomnia in the general population. Suvorexant has a novel mechanism of action. The first orexin-receptor antagonist on the market, suvorexant has been shown to improve sleep efficiency in healthy, non-elderly adults with primary insomnia (Herring 2012, Sun 2013). It is believed that suvorexant does not pose a risk of physical dependence or rebound insomnia as do the benzodiazepines and non-benzodiazepine soporifics (Bennett 2014).

Suvorexant may have other advantages that are of benefit specifically in the PD population. Suvorexant appears not to have a deleterious effect on next-day balance in healthy non-elderly subjects. This could be a significant advantage for suvorexant in patients with PD, who already have impaired balance and for whom, therefore, benzodiazepines may not be safe. In addition, suvorexant appears not to affect memory as measured by word recall. Again, this may be a distinct benefit in people with PD, who often have cognitive impairment as a result of their disease.

In addition to insomnia itself, people with PD have high rates of other conditions that may be improved by more efficient sleep, including depression and anxiety. REM behavior disorder (RBD), also experienced at high rates by people with PD, has limited treatment options. The effects of suvorexant in these ancillary conditions in PD are unknown and warrant study.

Suvorexant is approved at doses up to 20 mg daily (Prescribing Information, Merck 2015). Although this dose has been found to be safe in a healthy geriatric population, people with PD may be more sensitive to the therapeutic and adverse effects of suvorexant. It is also likely that subjects in a PD trial will be on other medications that may increase daytime somnolence. For these reasons, we are proposing a study of the 10-mg and 15-mg doses only. If suvorexant is found to be well-tolerated at a dose of 10 or 15 mg daily, future studies can explore the safety and efficacy of 20 mg daily in a PD population.

2.3 Wearable Sleep Monitors in Insomnia

The use of wearable sleep monitors has become increasingly common in the general population. However, the role these devices may play in diagnosing or monitoring insomnia and other sleep disorders is unknown. For this study, the FitBit Charge will be used. This device was chosen for its practicality and affordability, which makes it a device consumers are already using. Understanding how the feedback from this commonly used device relates to data from PSG and clinical ratings will be important in informing discussions with patients in the future.

3. STUDY OBJECTIVES & HYPOTHESES

3.1 Primary Objective

To assess the safety and efficacy of suvorexant in treating insomnia in Parkinson disease

3.2 Secondary Objectives

1. To assess the precision of a wearable sleep monitor in measuring total hours of sleep and WASO as compared to nocturnal polysomnogram (PSG).
2. To assess the effect of suvorexant on motor and non-motor symptoms of PD, including REM behavior disorder (RBD).

3.3 Primary Hypothesis

Suvorexant will provide greater improvement in sleep, as measured by polysomnographic parameters and symptom rating scales, compared to placebo, with no clinically significant increase in adverse events.

3.4 Secondary Hypotheses

1. On nights of PSG, total hours of sleep and WASO as measured by a wearable sleep monitor will not be significantly different from those values as measured by PSG.
2. Suvorexant will not worsen motor symptoms or non-motor symptoms of PD compared to placebo.

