7.4 Efficacy Assessment Based on Wearable Sleep Monitor

The secondary outcome measure based on the wearable sleep monitor (WSM) will include:

- Total hours of sleep per night, mean over final 7 nights of treatment period compared to mean over final 7 nights of screening period
- Wakefulness after sleep onset (WASO), mean over final 7 nights of treatment period compared to mean over final 7 nights of screening period

8. Statistical Methods

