8.5 Efficacy Analysis

Analysis of primary and secondary outcome measures will include:

- Summary statistics (n, mean, standard deviation, median, minimum and maximum) at baseline, Office Visit 3 and Office Visit 5 by treatment.
- For clinical rating scales, summary of % change from baseline to Office Visit 3, from baseline to Office Visit 5, and from Office Visit 4 to Office Visit 5, by treatment
- For PSG variables, summary of % change from PSG 1 to PSG 2 and from PSG 1 to PSG 3, by treatment

- For wearable sleep monitor, summary of % change in total hours of sleep and WASO. Mean over the week prior to Office Visit 2 (baseline) will be compared to the mean over the final week of Treatment Period 1 and to the mean over the final week of Treatment Period 2. Mean over the week prior to Office Visit 4 (during washout) will be compared to the mean over the final week of Treatment Period 2. This will be done by treatment arm.
- Significance testing

Outcome measures will be compared between groups using analysis of covariance (ANCOVA) or other method as deemed appropriate by the consulting statistician. Demonstration of superiority will depend on achieving statistical significance for the primary endpoint. Level of significance will be defined as $p = 0.05$. All statistical tests will be two-sided.

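### Secondary hypothesis 1 judges the wearable by a non-significant difference from PSG although the objective is precision, and no listed analysis pairs the two on the same night

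*Combined protocol and SAP*

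**What the plan says.** The first secondary objective (protocol 3.2) is "To assess the precision of a wearable sleep monitor in measuring total hours of sleep and WASO as compared to nocturnal polysomnogram (PSG". The matching hypothesis in 3.4 is that, on PSG nights, the two sleep variables "as measured by a wearable sleep monitor will not be significantly different from those values as measured by PSG". The synopsis (1.6.2) uses the same criterion: "will not be significantly different from those values as measured by PSG".

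The analyses listed for the wearable are of another kind. Section 7.4 (also 1.10.4) defines each wearable outcome as a "mean over final 7 nights of treatment period compared to mean over final 7 nights of screening period". Section 8.5 plans, "For wearable sleep monitor, summary of % change in total hours of sleep and WASO", by treatment arm, and 1.11 specifies that "Mean over the week prior to Office Visit 2 (baseline) will be compared to the mean over the final week of Treatment Period 1", with similar contrasts for Treatment Period 2 and the washout week. Both sections also carry a bare entry for significance testing and this sentence: "Outcome measures will be compared between groups using analysis of covariance (ANCOVA) or other method as deemed appropriate by the consulting statistician". Under 1.9.3 and 5.2.1, subjects who cannot or will not use the monitor correctly stay in the trial and "the observations from their WSM variables will be treated as missing data".

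**The concern.** The criterion does not match the objective. Precision concerns how far the device strays from PSG on a given night. A test of the mean difference does not measure that, because an overestimate on one night cancels an equal underestimate on another. Failing to reject in a small sample is not evidence of agreement either. When some bias exists, a noisier device or fewer usable pairs makes non-significance more likely, so the criterion favours the poorer measurement.

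No same-night comparison of device and PSG is specified, and nothing says how up to three PSG nights per subject would be handled. Section 2.3 says that knowing how this consumer device relates to PSG will matter when talking with patients. What is at stake is that an inconclusive test could be taken as reassurance about the device.

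**Working it through.** **Is a same-night comparison specified?** In every wearable contrast in 1.10.4, 1.11, 7.4 and 8.5, both sides are 7-night device means. None has a PSG value on either side. The overlap with PSG nights is as follows:

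- PSG 1: Office Visit 2 falls 7-14 days later (4.4.1), so the device baseline week can contain that night only at the 7-day edge.
- PSG 2 and PSG 3: each is the last night of its treatment period (4.4.5, 4.6.5), so it does fall inside the analysed week.

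Even in the second case, the PSG night is averaged with six others and is never set against the PSG value. The weekly means therefore cannot stand in for a paired comparison.

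**How would the stated criterion behave?** The plan has no figure to reproduce. Section 8.2 gives no power calculation, and no SD or agreement margin appears anywhere.

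Inputs from the documents: two-sided 0.05 (8.5), 20 subjects (8.2), three PSGs per subject (4.1).

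Assumptions: a paired t test, a true bias of 0.3 SD, between-night correlation ρ from 0 to 1, and 15 usable subjects as a lower case. SD means the SD of single-night device-minus-PSG differences.

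Let d = bias / SD. The probability of non-significance is F(t) − F(−t). Here F is the noncentral t distribution with n − 1 degrees of freedom and noncentrality d_eff·√n, and t is the two-sided 5% critical value (2.093 for n = 20). For one night d_eff = d. For the mean of three nights d_eff = d / √((1 + 2ρ)/3).

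| Case (one variable) | One night | Three nights, ρ = 0 / 0.5 / 1 |
|---|---|---|
| n = 20, zero bias, any SD | 0.950 | 0.950 / 0.950 / 0.950 |
| n = 20, d = 0.3 | 0.753 | 0.403 / 0.655 / 0.753 |
| n = 20, same bias, SD doubled (d = 0.15) | 0.902 | 0.803 / 0.878 / 0.902 |
| n = 15, d = 0.3 | 0.808 | 0.534 / 0.736 / 0.808 |

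For example, at n = 20 and d = 0.3 with one night, the noncentrality is 0.3 × √20 = 1.342. With three nights and ρ = 0, d_eff = 0.3 / √(1/3) = 0.520. The largest observed mean difference that stays non-significant with one night is 2.093/√20 = 0.468 SD.

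The hypothesis names two variables. If both must be non-significant, the one-night rate lies between the square of the single rate (independent errors) and the single rate itself (perfectly correlated errors). At zero bias this is 0.950² = 0.90 to 0.95. At 0.3 SD in both it is 0.753² = 0.57 to 0.75.

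**What would limits of agreement deliver?** With one pair per subject and n = 20, the 95% CI half-width of each limit is t·√(1/n + 1.96²/(2(n − 1))) = 2.093 × √(0.0500 + 0.1011) = 0.81 SD. With three nights per subject, simulation using the same t multiplier gives about 0.47 SD at ρ = 0, rising to 0.81 SD at ρ = 1.

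**The case against.** The plan is not closed to the right analysis. The significance-testing entry and the freedom to use another method leave room for a paired comparison. The monitor is to be worn throughout (4.3.1) and uploaded at Office Visits 2 to 5 (Appendix 11.1), so sleep-duration pairs could be analysed if nightly values are kept. The study is exploratory, superiority rests on the primary endpoint alone, and the magnitudes above rest on assumed inputs. All of this stands, and it limits the weight of the point. But room for an analysis is not a specification, and the only criterion written down is the wrong one for precision.

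A reader might infer several stronger things that the documents do not support:

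- That the investigators will claim agreement from p > 0.05. The hypothesis invites that reading, but no analysis section commits to it.
- That the weekly means miss the PSG nights altogether. Two of the three nights fall inside analysed weeks.
- That at most 20 subjects can contribute pairs. Withdrawn patients may be replaced (5.4) and all randomised patients are analysed (8.3). Missing wearable data may equally leave fewer than 20.
- That 95% or 75% is the chance that the whole hypothesis is upheld. Those rates are for one variable, and requiring both lowers them as shown.

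**Conclusion.** The point holds as a mismatch between objective and criterion, together with the lack of a specified same-night analysis. At zero bias the criterion carries no information about precision: each test is non-significant 95% of the time whatever the SD. That result needs no assumed bias or correlation, only a valid test of the mean at 0.05. The figures for a 0.3 SD bias are illustrations. The documents do not name the paired t test, the bias, the correlation or the averaging of nights, and nothing shows that 0.3 SD would matter to a patient. The change is worth making, but it is modest and concerns a secondary device objective in a pilot study.

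**What to change.** Reword hypothesis 1 in 1.6.2 and 3.4 as estimation of agreement. In 1.11 and 8.5, for total sleep time and for WASO separately, use every PSG night that has both records and report:

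- the mean device-minus-PSG difference with its 95% CI;
- the 95% limits of agreement with CIs, allowing for repeated nights within subject (for example through a random subject effect);
- the number of subjects and of nights with usable pairs.

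State that a non-significant difference will not be read as agreement, and that no agreement or equivalence verdict will be given unless a margin is prespecified.

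Secure the data. Export nightly device total sleep time, and export PSG total sleep time, which the minimum PSG report (4.3.2, 4.4.5, 4.6.5) does not list although it is the numerator of sleep efficiency (7.2.1). Export nightly device WASO if the device provides it. Section 4.3.1 names only sleep duration and sleep efficiency as calculated outputs. If the device does not provide WASO, state that the WASO comparison cannot be made.

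The cost is a change of wording, a small extra analysis and no new procedures. The limits will be imprecise, as shown in the working, and the result may be inconclusive.
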